## 8.2. Study assessments

### 8.2.1. Efficacy

Tumors will be assessed according to either RECIST version 1.1 guidelines by CT scan or MRI imaging of the target/non target lesions (38), and/or GCIG criteria using the serum marker CA-125 for Cohort 4, if applicable.(39)

CT scan and MRI will be performed at screening, then every 8 weeks ( $\pm$  1-week tolerance window) during the first 10 cycles, then every 12 weeks ( $\pm$  1 week) from Cycle 13 until symptomatic PD or confirmed iRECIST PD or start of any new cancer treatment or end-of-life care or end of the Main study period, whichever occurs first. For patients who exceptionally continue study treatment after completion of 13 cycles, tumor response assessments will continue at 12-week intervals ( $\pm$  1 week window) until the end of the Main study period, and thereafter at the frequency of local institutional care practice until PD, start of any new anticancer therapy, death or EOT.

Imaging will be performed as per site standard but whenever possible using contrast agent at screening and during treatment

CA-125 dosages will be performed at screening exclusively in patients included in Cohort 4. In case of abnormally elevated levels before treatment start, these dosages will be repeated on Day 1 of each subsequent cycle.

In case of response, efficacy assessments will be repeated 4 weeks later after first documentation (+ 1-week tolerance window). All patients will have an efficacy assessment (CT scan/MRI or serum CA-125 dosage) at the time of disease progression and/or treatment discontinuation, whichever occurs first.

As an exploratory analysis, tumor response will also be assessed using the iRECIST criteria (novel modified RECIST v1.1 guideline for immunotherapeutics).(40) These exploratory analyses will be described in the SAP.

Patients with asymptomatic, but radiologically observed unconfirmed PD as per iRECIST, may continue the study treatment, upon both the Investigator's request and the Sponsor's agreement, until PD is confirmed as per iRECIST or symptoms occurs or Investigator/patient decision to withdraw treatment, whichever occurs first.

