### 8.2.1.1. Measurability of tumor lesions

Patients must have at least one measurable tumor lesion, according to the RECIST version 1.1 criteria (38) and/or GCIG criteria (Cohort 4), if applicable.(39)

As per RECIST v1.1 guidelines, measurable tumor lesions must be measured in at least one dimension (longest diameter in the plane of measurement is to be recorded except for measurable lymph nodes) with a minimum size of:

- 10 mm by CT scan (slice thickness  $\leq 5$  mm)
- 10 mm caliper measurement by clinical exam (lesions which cannot be accurately measured with calipers should be recorded as non measurable)
- 20 mm by chest X-ray
- Malignant lymph nodes:  $\geq 15$  mm in short axis when assessed by CT scan (slice thickness  $\leq 5$  mm). Only the short axis is measured.

As per GCIG criteria (Cohort 4, if applicable), patients can be evaluated according to CA-125 only if they have a pretreatment sample that is at least twice the upper limit of the reference range and within 2 weeks before starting the treatment.

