#### 8.2.2.5. Safety laboratory

Safety laboratory measurements are scheduled at screening, C1D1 pre-treatment (only required if screening test were performed > 7 days prior to C1D1 or if inclusion/exclusion criteria were not met during screening),

on Days 3 (Part A only), 8, 15, 17 (Part A only), and 22 of Cycle 1, on Days 1 and 15 of Cycle 2 and 3, on Days 1 of any other subsequent cycle and at EOT. On dosing days, samples will always be collected predose and results reviewed prior to nivolumab infusion, if applicable. All measurements will be performed locally.

On Days 3 and 17 of Cycle 1 for patients included in Part A only, serum will be collected and measured for total bilirubin (if >ULN: direct bilirubin should also be measured), alkaline phosphatase (ALP), AST, ALT and creatinine.

For all other visits mentioned above, blood/serum will be measured for the following panels:

- **Hematology:** Hemoglobin, hematocrit, complete blood count (incl. differential) and platelets
- **Chemistry:** Creatinine, sodium, potassium, calcium, total bilirubin (if >ULN: direct bilirubin should also be measured), ALP, AST, ALT, amylase, lipase, lactate dehydrogenase (LDH), total protein, albumin and C-reactive protein (CRP)

In addition, the following laboratory measurements will be collected:

- on Days 1 and 15 of Cycle 1 and Days 1 of each subsequent cycle:

TSH, free triiodothyronine (FT3), free thyroxine (FT4),

- At screening, the following will also be measured: HIV, HBV, and HCV serology, CPK and troponins, FSH/LH and total testosterone (in males) or estrogens (in pre-menopausal female patients, meaning those whose last menstruation occurred within 12 months of screening date), free-cortisol (at morning) and ACTH. These dosages could be repeated if clinically indicated.

For applicable patients included in Cohort 4, CA-125 dosages will be performed at screening within 4 weeks of C1D1 and will be repeated on Day 1 of each subsequent cycle, if abnormally elevated levels are obtained before treatment start. Patients are evaluable as per GCIG criteria only if they have a pretreatment sample that is at least twice the upper limit of the reference range and within 2 weeks before starting the treatment.

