- 1 Digital triplicate 12-lead ECGs will be recorded after 10 minutes of supine rest at the following 3 time points: pre-, 0.5-2h Debio 1143 post-dose (before starting the nivolumab infusion or after nivolumab perfusion was removed) and 4-6 h post-dose; There should be at least 1 minute between each ECG and all 3 ECGs should be completed within 10 minutes or less. ECG readings must be performed before PK/PDy sampling. ECG reading will be done centrally and also locally for screening purposes.
- 2 Pre-dose (as per section 8.2.2.5) only required if screening test were performed > 7 days prior to C1D1 or if inclusion/exclusion criteria were not met during screening:
- 2a HIV, HCV and HBV serology testing and CPK and Troponins (I or T whichever is applicable): Only at screening, to be repeated if clinically indicated only.
- 2b FSH/LH and total testosterone (in male) or estrogens (in female patients), free-cortisol (at morning) and ACTH: Only at screening and to be repeated if clinically indicated.
- 2c Hemoglobin, hematocrit, platelets and complete blood cell count and differential counts, creatinine, sodium, potassium, calcium, total bilirubin (if >ULN, then also measure direct bilirubin), ALP, AST, ALT, amylase, lipase, LDH, total protein, albumin, CRP.
- 2d Part A patients (only): Total bilirubin (if >ULN, then direct bilirubin should also be measured), ALP, AST, ALT, and creatinine.
- 2e TSH, FT3 and FT4: At Day 1 and Day 15 in Cycle 1 and every Day 1 of each subsequent cycle.
- 2f CA-125 to be performed at screening within 4 weeks of C1D1, exclusively in applicable patients included in Cohort 4, and to be repeated before start of each new cycle if abnormally elevated before treatment start, unless PD, any new anticancer treatment or end-of-life hospice care is started before.
- 3 In women of childbearing potential only: blood test at screening (only required if screening test were performed > 7 days prior to C1D1), then urine dipstick test alone would be sufficient, at the beginning of each treatment cycle while on study up to 5 months after EOT.

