##### Definition of PFS and duration of response by CA-125

PFS based on CA-125 will be defined as the time from first study drug infusion until the GCIG-Rustin-modified criteria of progression are met, or until the date of death (with or without disease progression). Duration of CA-125 response will be defined as the time between when the CA-125 was first documented to have decreased by 50% in a patient who meets all the GCIG-Rustin-modified criteria for a CA-125 response, and the time the CA-125 is first documented to have risen to the point where the patient meets GCIG criteria of disease progression.

GCIG-Rustin-modified definition of progressive disease according to CA-125 criteria		
	Definition of progression	Date of progression
Patients with elevated CA-125 before treatment and normalization of CA-125 during treatment	CA-125 $\geq$ 2 X ULN documented on 2 occasions**	Date CA-125 is first elevated to $\geq$ 2 X ULN
Patients with elevated CA-125 pretreatment that never normalizes	CA-125 $\geq$ 2 X nadir value on 2 occasions**	Date CA-125 is first elevated to $\geq$ 2 X nadir value
Patients with CA-125 in normal range pretreatment	CA-125 $\geq$ 2 X ULN documented on 2 occasions**	Date CA-125 is first elevated to $\geq$ 2 X ULN

\*\*Repeat CA-125 anytime but normally not less than 1 week after the first elevated CA-125 level. CA-125 levels in samples obtained after administration of mouse antibodies or within 4 weeks after surgery or paracentesis should not be taken into account.

In patients for whom response to treatment is evaluated by both RECIST and CA-125 criteria, the date of response and progression will be the earliest date of the two methods.

¶Adapted from Rustin et al, 2004 (41)

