17.1.1. PRIMARY EFFICACY VARIABLE & DERIVATION

The primary efficacy variable is confirmed ORR as per RECIST v1.1 and/or CGIG criteria (cohort 4, if applicable).

Confirmed objective response as per RECIST v1.1 is a confirmed best overall response (cBOR) of partial response (PR) or complete response (CR). The full derivation of confirmed BOR is included in Section 17.2.1.2.

In the situation of lack of RECIST evaluation data (cohort 4 only), confirmed objective response as per GCIG criteria will be done using CA-125 levels. Patients will be scored as having attained a CA-125 response if they meet the GCIG-Rustin-modified criteria which require that there is at least a 50% reduction in CA-125 levels from a pre-treatment sample. The response must be confirmed and maintained for at least 28 days. Patients can be evaluated according to CA-125 only if they have a pre-treatment sample that is at least twice the upper limit of normal and within 2 weeks prior to starting treatment.

Document: T:\sas\Debiopharm\Debio_1143\CZA60507\Biostatistics\Documentation\SAP\SAP Text\V5

Author: [REDACTED] Version Number: 5.0
Version Date: 19APR2022

Template No.: CS_TP_BS016 Revision 5
Effective Date: 01Apr2018

Reference: CS_WI_BS005

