----------------------------------------------------	---------------------------------------------------	-------------------------------------------------

**Repeat CA-125 anytime but normally not less than 1 week after the first elevated CA-125 level. CA-125 levels in samples obtained after administration of mouse antibodies or within 4 weeks after surgery or paracentesis should not be considered.

In patients for whom response to treatment is evaluated by both RECIST and CA-125 criteria, the RECIST evaluation will be used.

The median PFS and the PFS rate at each months will be derived from the Kaplan-Meier curves, as described in section 7.6.

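### Cohort 4: the baseline CA-125 may be drawn up to 4 weeks before first dose, but the primary endpoint accepts it only within 2 weeks

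*Protocol*

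**What the plan says.** **When the sample is drawn.** Protocol 8.2.2.5: "CA-125 dosages will be performed at screening within 4 weeks of C1D1". The measurements then "will be repeated on Day 1 of each subsequent cycle, if abnormally elevated levels are obtained before treatment start". Footnote 2f of Table 8-6, repeated in Table 1-1, agrees: "CA-125 to be performed at screening within 4 weeks of C1D1, exclusively in applicable patients included in Cohort 4". In both tables code 2f stands at screening and on Day 1 from Cycle 2 onward. The C1D1 column carries codes 2c and 2e only.

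**When the sample counts.** Protocol 8.2.1.1 allows assessment by CA-125 "only if they have a pretreatment sample that is at least twice the upper limit of the reference range and within 2 weeks" before treatment starts. The last sentence of 8.2.2.5 and Appendix C repeat the rule. SAP 17.1.1 applies it to confirmed response: the sample must be "at least twice the upper limit of normal and within 2 weeks prior to starting treatment".

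**Who depends on it.** Inclusion criterion 7 accepts Cohort 4 patients on GCIG criteria and names no sampling window. Section 8.2.1.2 assigns CA-125 to Cohort 4 patients without RECIST-measurable disease. SAP 6.5 removes patients without measurable disease by RECIST or GCIG from the efficacy set (category 2) and has them replaced.

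**Two related places.** Protocol 8.2.1 says: "All patients will have an efficacy assessment (CT scan/MRI or serum CA-125 dosage) at the time of disease progression and/or treatment discontinuation", whereas the EOT column of the schedule has codes 2c and 2e but not 2f. For patients followed by both methods, Appendix C says "the date of response and progression will be the earliest date of the two methods", while SAP 17.2.1.5 says "the RECIST evaluation will be used".

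**The concern.** The schedule permits a baseline sample that the endpoint definition rejects, and no later draw before first dose is required. A patient who relies on CA-125 and is sampled in the early part of screening has done everything the schedule asks, yet has no valid baseline for the primary endpoint.

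At stake is treatment of a patient who cannot contribute a CA-125 response. Either the patient should not have been enrolled, or the patient is removed from the primary set after treatment and another is enrolled in the same place. Evaluability also decides who counts among the first 8 and first 11 patients at the futility looks, where a single response can decide whether the cohort continues.

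**Working it through.** This is a comparison of a sampling window with an evaluability window. No power or boundary figure is in dispute.

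**Step 1. Is there another pre-dose draw?** Section 8.2.2.5 requires C1D1 safety laboratories if the screening tests are more than 7 days old or eligibility was not met at screening. The hematology and chemistry panels listed there do not include CA-125, and the C1D1 column has no 2f. Footnote 2f speaks of repeats before each new cycle, which might be stretched to Cycle 1. But the tables do not place it there, and 8.2.1 and 8.2.2.5 both speak of subsequent cycles. So no scheduled draw closes the gap.

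**Step 2. Count the days.**
- Permitted days: Day -28 to Day -1 = 28.
- Days meeting the 2-week rule: Day -14 to Day -1 = 14.
- Days outside it: Day -28 to Day -15, 28 - 14 = 14, so 14/28 = 50% of permitted days.
- If the schedule's general Day -32 tolerance also applies to CA-125: 32 - 14 = 18, so 18/32 = 56%.
- If a sample within 14 days of C1D1 were required: 0 days outside.

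These are shares of calendar days, not of patients.

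**Step 3. What happens to a CA-125-only patient sampled on Day -28 to -15?**
- If the 2-week rule is part of GCIG measurability (it stands in the measurability section, 8.2.1.1), the patient fails criterion 7. If treated anyway, the patient meets SAP category 2b and is excluded and replaced.
- If the rule is not part of measurability, the patient is eligible and may stay in the efficacy set. SAP 17.1.1 still bars assessment by CA-125, so the patient cannot count as a CA-125 responder.

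Both readings give a bad result from a schedule followed exactly.

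**Step 4. Size.** Let g be the share of Cohort 4 relying on CA-125 and s the share of those sampled too early. The documents give neither. If replacements come from the same mix, the unevaluable fraction is d = g × s, and reaching 15 evaluable patients needs about 15/(1 - d) enrolled. With s = 0 this is 15 for any g. With s = 1, the upper extreme:
- assumed g = 0.10: 15/0.90 = 16.7, so 17
- assumed g = 0.25: 15/0.75 = 20
- assumed g = 0.50: 15/0.50 = 30

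The range is wide because g and s are unknown. It is not an estimate.

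**Step 5. Decision rules.** With the Beta(0.5, 0.5) prior, P(θ ≤ 0.05) is 0.643 at 0/8 and 0.223 at 1/11, both above 0.2. It is 0.149 at 1/8 and 0.041 at 2/11, both below. P(θ > 0.15) is 0.892 at 4/15 and 0.726 at 3/15, against 0.8. The plan's boundaries reproduce. They are set on evaluable counts and are unaffected here.

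**The case against.** The strongest reply is that the windows are nested, not contradictory. A site can satisfy both by sampling in the last 14 days, and the 2-week rule stands in the same paragraph as the 4-week window. If criterion 7 takes its meaning from 8.2.1.1, an early-sampled patient is simply ineligible, and all that is missing is a cross-reference. Part of this stands: no site is forced into the problem, and the defect is one of wording. But permitting a valid sample does not secure one. Under that reading the schedule still leads a compliant site to an ineligible patient, with no redraw specified.

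It is also fair that few patients may be affected. SAP 17.1.1 uses CA-125 only where RECIST data are lacking, and the tumor list in 8.2.1.2 omits cervical cancer. Excluded patients are replaced, and all treated patients stay in the ITT sensitivity analysis (SAP 17.1.4).

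Four stronger readings are tempting, and the documents do not support them.
- *Half of CA-125-only patients will be lost.* That needs sampling spread evenly over screening, which nothing in the plan states. The possible range is 0% to 100%.
- *CA-125 is never measured at end of treatment.* Protocol 8.2.1 and 11.4.1.1 call for CT/MRI or CA-125 at progression, 8.2.1 also at discontinuation, and 8.2.1.2 asks for monthly CA-125. The EOT column is a mismatch between table and text.
- *PFS and duration of response cannot be observed in these patients after treatment.* Death is an event for both (SAP 17.2.1.5 and 17.2.1.6), SAP 17.1 also counts clinical and radiological progression, and Protocol 8.3.2.2 continues imaging and clinical assessment every 12 weeks.
- *The cohort ends with fewer than its planned evaluable patients.* Replacement (Protocol 6.3, SAP 4.1.2) prevents that.

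**Conclusion.** The point holds as a misalignment between the baseline CA-125 schedule and the evaluability rule for the primary endpoint, limited to Cohort 4 patients who rely on CA-125. It covers 14 of 28 permitted sampling days (18 of 32 if the tolerance applies). The consequence is avoidable exposure, extra enrolment and exclusion from the primary set after treatment, with the evaluable number preserved. Category 2b follows if the 2-week rule defines GCIG measurability, which its place in 8.2.1.1 supports. If it does not, the patient still cannot be scored by CA-125. The change is worth making because it is specific and nearly free.

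Two secondary inconsistencies are real but separate: the EOT column against 8.2.1, and the dating rule in Appendix C against SAP 17.2.1.5. The second concerns patients followed by both methods and affects secondary endpoints. Protocol 11.6 leaves the definitive analysis to the SAP, so the operative rule is known, but SAP 4.3 does not list the change.

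**What to change.** 1. In footnote 2f (Tables 1-1 and 8-6) and section 8.2.2.5, require for patients relying on GCIG criteria a CA-125 sample within 2 weeks before C1D1. Repeat it if the screening sample is older, with the result known before first dose. SAP 7.2 already takes the last pre-treatment value as baseline, so the derivation need not change.
2. State the same window, and the requirement of at least twice the upper limit, in inclusion criterion 7 (section 6.1 and synopsis).
3. Reconcile the EOT column with section 8.2.1.
4. Choose one dating rule for patients assessed by both methods, align Appendix C and SAP 17.2.1.5, and record the change in SAP 4.3.

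SAP 4.3 already reports futility of the Part B cohorts. If recruitment has ended, the useful step is to list the baseline CA-125 date of each CA-125-only patient and any exclusion that followed from it.

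**Cost.** Items 1 and 2 need wording and at most one repeat assay in a few patients. Item 4 is wording only. Item 3 is wording, or one CA-125 assay at a visit that already has blood sampling. No CA-125 draws at follow-up visits are proposed.

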#### 8.2.2.6. Pregnancy test

For WOCPBP, a serum test measuring  $\beta$ -HCG will be performed at screening. A predose urine pregnancy test at the beginning of each cycle (at C1D1 only required if screening test were performed > 7 days prior to C1D1) will be performed as well while on treatment and up to 5 months after of the last study dose, if patients is ongoing follow up.

#### 8.2.3. Pharmacokinetics

PK samples will be collected as described below for determination of Debio 1143 and Debio 1143-MET1 plasma concentration, and of nivolumab serum concentrations. In addition, samples will be collected to allow for determination of nivolumab anti-drug antibodies (ADA), if deemed appropriate to support PK data interpretation. After completion of the analysis, the remaining PK samples may be stored for up to a maximum of 15 years after the end of the study and, if required, may be used for metabolic profiling, for further bioanalytical investigations (such as method cross-validation and protein binding), for a retrospective examination of safety laboratory tests or proteins involved in the metabolism or the pharmacological effects of Debio 1143 or nivolumab.

For all PK samples, exact sampling time must be recorded. PK samples will be taken in both parts of the study but will differ depending on the administration schedule of nivolumab (i.e., every 15 days throughout the study or every 4 weeks after Cycle 2).

Sampling days and times for PK are listed in: [Table 8-1](#), [Table 8-2](#) and [Table 8-3](#).

- For the determination of Debio 1143 and Debio 1143-MET1, during Cycle 1 PK samples are to be collected for Part A on Days 1, 3, 8, 15, 17 and 22 and for Part B on Days 1, 8, 15 and 22. During Cycle 3, PK samples will be collected for Part A on Days 1, 3, 15 and 17 and for Part B on Days 1 and 15. During Cycle 6 on Day 1 (in both parts A and B). On Days 1, 8, 15, and 22 of Cycle 1, and on Days 1 and 15 of Cycle 3 there are at least two PK samplings on the same day. Samples will be analyzed for Debio 1143 and Debio 1143-MET1 using a validated LC/MS/MS method with a lower limit of quantification (LOQ) of 2.5 ng/mL for both compounds.
- For the determination of nivolumab, during Cycle 1 PK samples are to be collected for Part A on Days 1, 3, 8, 15, 17 and 22 and for Part B on Days 1, 8, 15 and 22. During Cycle 3, PK samples will be collected for Part A on Days 1, 3, 15 and 17 and for Part B on Days 1 and 15. During Cycle 6 on Day 1 (in both parts A and B). On Days 1 and 15 of Cycles 1 and 3 there are at least two PK samplings on the same day. Nivolumab serum concentrations will be determined using a validated electrochemiluminescence (ECL) immunoassay with a lower LOQ of 100 ng/mL.
- For ADA, blood is taken predose on Days 1 and 15 of Cycle 1 and 3, on Day 1 of Cycles 6 and at EOT for both Parts A and B. For patients entering the Extended study period, the last nivolumab ADA will be collected at C13D1 instead of at EOT.

If deemed appropriate to support PK data interpretation, samples will be analyzed for serum ADA entities using a validated immunoassay following a tiered testing approach.

For all PK measurements, the windows of tolerance for sample collection are provided in [Table 8-5](#).

**Table 8-1 Sampling days and times for PK on Cycle 1**

Cycle day	Cycle 1																		
	1					3	8				15					17	22		
Time [h]	0*	0.5 	1.5 	4 	8 	0*	0*	1.5	4 	8 	0*	0.5 	1.5 	4 	8 	0*	0*	1.5	4 
Part A																			
Nivolumab PK	X	-	X	-	X	X	X	-	-	-	X	-	X	-	X	X	X	-	-
Debio 1143 PK	X	X	X	X	X	X	X	X	X	X	X	X	X	X	X	X	X	X	X
Nivolumab ADA	X	-	-	-	-	-	-	-	-	-	X	-	-	-	-	-	-	-	-
Part B																			
Nivolumab PK	X	-	X	-	-	-	X	-	-	-	X	-	X	-	-	-	X	-	-
Debio 1143 PK	X	-	X	X	-	-	X	X	-	-	X	-	X	-	-	-	X	X	X
Nivolumab ADA	X	-	-	-	-	-	-	-	-	-	X	-	-	-	-	-	-	-	-

\* To be performed prior to Debio 1143 administration; At the time of the safety laboratory assessment;

 Just before start of nivolumab infusion;

 At the end of nivolumab infusion;

 4 hours after Debio 1143 administration;

 8 hours after Debio 1143 administration.

